4.1.9. Amyloid Disclosure Assessments

The Concerns about Alzheimer’s Disease Dementia Scale and the Future Time Perspective Scale are conducted for all subjects during the screening phase prior to and after the amyloid status disclosure visit and at regularly scheduled visits during the double-blind phase. For subjects with a PET scan performed to assess eligibility, the Views and Perceptions of Amyloid Imaging Scale will be assessed during the screening phase prior to and after the amyloid status disclosure visit. The Impact of Events Scale will be assessed for all subjects during screening after the amyloid status disclosure visit.

Concerns about Alzheimer’s Disease Dementia Scale

See Section 5.5.1.1 for details about the Concerns about Alzheimer’s Disease Dementia Scale. The distribution of item scores, which range from 1 (strongly agree) to 5 (strongly disagree), for each of the 6 questions will be summarized by treatment group and overall for the pre- and post-amyloid status disclosure visits.

Future Time Perspective Scale

See Section 5.5.1.1 for details about the Future Time Perspective (FTP) Scale and calculation of the overall FTP score. Overall FTP score will be summarized with descriptive statistics by treatment group and overall for the pre- and post-amyloid status disclosure visits.

Impact of Events Scale

The Impact of Events (IES) scale is a 15-item self-report measure that assesses 2 common responses related to a specific stressful life event: intrusion and avoidance³. The IES has been adapted for amyloid disclosure-related distress. The scale will be administered during the screening phase within 3 days after disclosure of amyloid status.

Subjects will rate how frequently each item was true for them since disclosure of amyloid results as “not at all” (0), “rarely” (1), “sometimes” (3), or “often” (5). The Intrusion sub-scale is the sum of the scores of the 7 intrusion-related items and the Avoidance sub-scale is the sum of the scores of the 8 avoidance-related items (see [Attachment 4](#) for a list of which items belong to which sub-scale). The total score is the sum of all 15 items. If any item is missing, the relevant sub-scale and the total score will be missing.

The total IES score and the Intrusion and Avoidance subscales will be summarized with descriptive statistics by treatment group and overall.

Views and Perceptions of Amyloid Imaging Scale

Subjects undergoing amyloid PET imaging to determine study eligibility will complete the Views and Perceptions of Amyloid Imaging scale during the screening phase prior to and after the amyloid status disclosure visit. Subjects will rate how important 9 reasons for seeking results of amyloid PET imaging are to them on a 5-point scale with 0 = “not at all important” to 5 = “extremely important”. The distribution of scores for each item will be summarized by treatment group and overall for the pre- and post-amyloid status disclosure visits.

4.2. Disposition Information

Screened subjects and reason for screen failures will be summarized overall.

The number of subjects in the following disposition categories will be summarized throughout the study by treatment group and overall:

- Subjects randomized
- Subjects receiving study medication
- Subjects completing the study
- Subjects who discontinued study medication
- Reasons for discontinuation of study medication
- Subjects who terminated study prematurely
- Reasons for termination of study

4.3. Treatment Compliance

Study medication compliance will be calculated as follows: Study medication compliance (%) = $100 \times \text{number of days taking study medication} / \text{total treatment duration (including days off study medication)}$. For subjects who continue in the double-blind phase after discontinuing study medication, compliance will be based only on the days up to the last day of study medication dosing.

The number and percentage of subjects who have at least 85% study medication compliance will be summarized by treatment group.

4.4. Extent of Exposure

The number and percentage of subjects who receive study medication will be summarized by treatment group.

Study medication duration is defined as: $(\text{date of last dose of study medication} - \text{date of first dose of study medication}) + 1$.

Descriptive statistics for study medication duration (N, mean, SD, median, and range (minimum, maximum)) will be presented by treatment group for the safety analysis set. Subject-years of exposure are calculated as days of exposure/365.25. Subject-years will be presented by treatment group.

Duration of exposure will be summarized in the following duration categories by treatment group and presented graphically in a histogram:

- <6 months (<180 days)
- 6 months - <1 year (181 to <365 days)
- 1 year – <1.5 years (365 to <548 days)
- 1.5 years - <2 years (548 to <730 days)
- 2 years - <2.5 years (730 to <913 days)

Cumulative exposure (≥ 6 months, ≥ 1 year, ≥ 2 years) will also be summarized.

4.5. Protocol Deviations

In general, the following list of major protocol deviations may have the potential to impact subjects' rights, safety or well-being, or the integrity and/or result of the clinical study. Subjects with major protocol deviations will be identified prior to database lock and the subjects with major protocol deviations will be summarized by category:

- Developed withdrawal criteria but not withdrawn
- Entered but did not satisfy criteria
- Received wrong treatment or incorrect dose
- Other

A listing of major protocol deviations will be provided.

4.6. Prior and Concomitant Medications

Prior and concomitant medications will be coded using the World Health Organization Drug Dictionary (WHO-DD). Prior medications are defined as any therapy used before the day of first dose of study medication. Concomitant medications are defined as any therapy used on or after the same day as the first dose of study medication, including those that started before and continued on after the first dose of study medication. Rules for handling partial concomitant medication start and stop dates are in [Attachment 5](#).

Summaries of concomitant medications will be presented by Anatomical-Therapeutic-Chemical (ATC) class and treatment group. The proportion of subjects who receive each concomitant medication will be summarized as well as the proportion of subjects who receive at least one concomitant medication. For subjects who continued in the double-blind phase after discontinuing study medication, separate summaries of concomitant medications taken while on study medication and after discontinuing study medication will be provided.

Prior medications will be summarized by treatment group and ATC class.

5. EFFICACY

Inferential analyses or descriptive analyses will be performed for the on-treatment period. For off-treatment period, only descriptive statistics will be presented.

5.1. Analysis Specifications

5.1.1. Level of Significance

At the time of cessation of dosing, 34% of the planned 1650 subjects had been randomized and 80% of those randomized had no more than 12 months of the planned 54 months of treatment. As a result, any statistical comparisons will be considered exploratory in nature and will be performed at the 0.05 level of significance without adjustment for multiple comparisons.

5.1.2. Data Handling Rules

Missing data handling rules will be applied to the scales that are included in the composite primary efficacy endpoint (see Section 5.2.2). For on-treatment visits, if a scale value is missing and the scale value was observed at the previously scheduled visit, the value at the previous visit will be carried forward. If a scale value is missing at baseline and the scale value was observed at the next scheduled visit, the value at that visit will be used as the baseline value. No observation will be carried forward or backward more than one visit. Missing data in the off-treatment period will not be imputed.

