## Footnotes:

- a Screening assessments may be performed over multiple visits over a period of 90 days prior to dosing, with the determination of inclusion and exclusion criteria occurring over Visits 1 through 5. If needed for biomarker collection or interpretation, or for logistical reasons, this period can be prolonged with written approval from the sponsor. Steps III and IV assessments may only be performed after Steps I and II assessments relevant for determination of eligibility are done and if, based on the results, the subject is eligible for continued participation. The order of individual assessments within a step is not fixed, unless indicated otherwise. Different screening assessments associated with each step may be performed on a single visit day or spread over multiple visit days. Eligible subjects based on Steps I to IV assessments will return during the screening phase to the site to have part of their baseline cognitive and functional measures performed between Day -10 and Day -5 and at least 2 days post amyloid disclosure. Although visit numbers are specified, fewer or additional visits can occur based on the above, and the numbering is considered guidance.
- b This visit will be performed once Step IV results are available and must take place at least 2 days prior to the baseline cognitive assessments.
- c The Informant should sign an ICF or equivalent document prior to completing any informant related study procedures.
- d Dermatological examination performed by a dermatologist (as defined in Section 9.1.2) with photography (taken by dermatologist or qualified designee) it is preferred that the dermatology exam be conducted before Step III, but it must be conducted before amyloid testing
- e The Assessment of Psychological Well Being will consist of the State-Trait Anxiety Inventory only at screening, as the GDS short version will be extracted from the GDS.
- f Including coagulation, vitamin B12, and folic acid.
- g Only for those subjects having a PET scan performed to assess eligibility.
- h Administered by phone (or at a visit) within 3 days post amyloid disclosure visit.
- i In order to assess for and mitigate practice effects, the PACC, RBANS, NAB-DLTs for Memory and Attention, and computerized cognitive battery must be performed once during the screening period but (1) prior to Step IV assessments, (2) no later than Day -20.

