2.4. Visit Windows

As subjects do not always adhere to the protocol visit schedule, the following rules are applied to assign actual visits to analysis visits. Listed below are the visit windows and the target days for each visit. The same definitions will apply to visits before or after the treatment end date using the Analysis Day as defined in Section 2.3 above. The time period description will be appended with '(On-Trt)' for post-baseline visits on or prior to the treatment end date. The time period description will be appended with '(Off-Trt)' for post-baseline visits after the treatment end date. If a subject has 2 or more actual visits in one visit window, the visit closest to the target day will be used as the protocol visit for that visit window. The other additional visit(s) will not be used in the summaries or analyses but they can be used for determination of clinically important endpoints. If 2 actual visits are equidistant from the target day within a visit window, the later visit will be used.

All assignments will be made in chronological order. Once a visit date is assigned to a visit window, it will no longer be used for a later time point except for the endpoint. Listed below (Table 1) are the visit windows and the target days for each visit defined in the protocol.

Table 1: Visit Windows for on and off-treatment Analysis

Scheduled Visit Number	Time period (label on output)	Time Interval (Day*)	Target Time Point (Day)
7	Baseline	-120 to 1	1
8	Week 2	2 to 22	15
9	Week 4	23 to 36	29
10	Week 6	37 to 50	43
11	Week 8	51 to 64	57
12	Week 10	65 to 81	71
13	Month 3	82 to 106	92
14	Month 4	107 to 134	120
15	Month 5	135 to 165	148
16	Month 6	166 to 211	183
17	Month 8	212 to 256	239
18	Month 9	257 to 288	274
19	Month 10	289 to 333	302
20	Month 12	334 to 410	365
21	Month 15	411 to 501	456
22	Month 18	502 to 592	547
23	Month 21	593 to 683	638
24	Month 24	684 to 774	729
25	Month 27	775 to 865	820
26	Month 30	866 to 956	911
27	Month 33	957 to 1047	1002
28	Month 36	1048 to 1138	1093
29	Month 39	1139 to 1229	1184
30	Month 42	1230 to 1320	1275
31	Month 45	1321 to 1411	1366
32	Month 48	1412 to 1502	1457
33	Month 51	1503 to 1593	1548
34	Month 54	1594 to 1684	1639
	Month >54	1685 to ∞	1685

* Relative to analysis reference start date if visit date is prior to or on the treatment end date. Relative to treatment end date if visit date is after treatment end date.

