5.2.2. Definition

The primary endpoint is the PACC change score.

The PACC change score at a time point is a composite of 4 standardized changes from baseline (two episodic memory tests, one timed executive function test, and a test of global cognition) at that time point as follows:

PACC change score = $Z1+Z2+Z3+Z4$, where

- $Z1 = (\text{change from baseline in FCSRT score} / \text{SD of the baseline FCSRT score})$, where the FCRST score is twice the number of correct free recalls in 3 trials plus the number of correct cued recalls in 3 trials from the Free and Cued Selective Reminding Test (FCSRT). See Section 5.4.1.1 for details of the FCSRT.
- $Z2 = (\text{change from baseline in WMS test score} / \text{SD of the baseline WMS test score})$, where the WMS test score is the total number of correct recalls after a 30-minute delay from the Wechsler Memory Scale (WMS) Logical Memory subtest (delayed paragraph recall). See Section 5.4.1.2 for details of the WMS Logical Memory subtest.
- $Z3 = (\text{change from baseline in DSS test score} / \text{SD of the baseline DSS test score})$, where the DSS test score is the number of correctly drawn symbols completed in 120 seconds from the Wechsler Adult Intelligence Scale (WAIS)-IV Coding subtest (also known as the Digit Symbol Substitution [DSS] test). See Section 5.4.1.3 for details of the WAIS-IV Coding subtest.
- $Z4 = (\text{change from baseline in MMSE total score} / \text{SD of the baseline MMSE total score})$, where the MMSE total score is the total number of correctly completed items on the Mini-Mental State Examination (MMSE). See Section 5.4.1.4 for details of the MMSE.

The PACC baseline score is the sum of the 4 components' standardized baseline value (baseline value / SD of baseline values). The PACC scores will be considered missing if more than 1 of its 4 components is imputed (see Section 5.1.2). Change from the off-treatment baseline (see Section 2.4) will be calculated. For off-treatment visits, however, the components will not be imputed. The PACC scores will be considered missing if any of the components is missing.

The scales contributing to the PACC all follow the same schedule: during screening, at the randomization visit, and every 6 months after randomization through Month 54 (or early termination).

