5.2.3. Analysis Methods

The primary analysis is based on the primary analysis set defined in Section 5.2.1 and uses an MMRM model. This relies on the Missing at Random (MAR) assumption: after accounting in the model for the effects of the covariates and for the available efficacy scores, the unobserved data have the same distribution as the observed data.

The PACC change score will be analyzed by an MMRM model based on observed data at on-treatment visits. The fixed terms for this model are treatment group, sex, country, APOE ε4 carrier status, education level, PACC baseline score, age at study entry, average hippocampal volume at baseline, time point (as a factor), and the interaction of treatment and time point. Subject is included as a random effect.

Comparisons between each atabecestat dose group and placebo will be performed at Months 6, 12, and 18 by using the appropriate contrasts based on this model. The Kenward-Roger approximation will be used to estimate the denominator degrees of freedom. Between-treatment differences in LS Means with the corresponding 95% confidence intervals (CIs) and p-values will be provided. If the unstructured covariance matrix results in a lack of convergence, starting values will be supplied using estimates from simpler structures. If this strategy does not result in

convergence then the following structures will be used in sequence: heterogeneous autoregressive of order 1 (ARH(1)), heterogeneous compound symmetry (CSH), and homogeneous compound symmetry (CS).

Plots of mean (\pm SE) PACC change score over time by treatment group will be provided for observed data and for estimates based on the MMRM.

For the off-treatment period, change of PACC and the components from off-treatment baseline will be summarized.

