5.3. Key Secondary Endpoint

5.3.1. Definition

The key secondary efficacy endpoint is the change from baseline in the subject-reported Cognitive Function Index (CFI) total score. The CFI is a modified version of the Mail-in Cognitive Function Screening Instrument²⁰, a subject- and informant-reported outcome measure developed by the ADCS. The subject-reported and informant-reported CFIs are assessed on the same schedule: 5 to 10 days before randomization, then annually after randomization through Month 48, and at Month 54 (or early termination if not performed at previous visit). This assessment includes 14 questions that assess the subject's perceived ability to perform high-level functional tasks in daily life and sense of overall cognitive functional ability (yes=1; no/does not apply=0; maybe=0.5 for each question) and 1 additional question about whether the subject has seen a doctor in the last year about memory concerns. Study subjects and their informants independently rate the subject's abilities.

The CFI total score is the sum of the first 14 questions, with higher scores indicating greater impairment (range = 0 to 14). If there are fewer than 5 (<30%) missing items, an imputed total score will be calculated as a prorated total based on the observed items:

$$14 * \left(\frac{\text{Total score of non-missing items}}{\text{Total number of non-missing items}} \right)$$

Imputed total scores will be rounded to 1 decimal place. If there are 5 or more missing items, the total score will be missing. A subject-reported and an informant-reported total score will be calculated. Change from baseline in the CFI total score will be calculated at each time point. For off-treatment visits, change from the off-treatment baseline (see Section 2.4) will also be calculated.

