5.4.2. Analysis Methods

Analyses of the changes from baseline of each of the 4 PACC components, the changes from baseline of each of the 5 RBANS index scores, the change from baseline of the RBANS Total Scale, changes from baseline in informant-reported CFI total score, and change from baseline in ADCE-ADL-PI total scores (both the subject- and informant-reported) will be performed using a similar MMRM model as described above for the primary efficacy endpoint (Section 5.2.3). For each endpoint, baseline score in the model will be the baseline score for the given endpoint. For endpoints measured at unequally spaced time points, time (month) will be included as a continuous variable. For the individual PACC components, summaries based on both the original and standardized scale will be provided. For off-treatment period, changes from the off-treatment period baseline will be summarized.

For other secondary efficacy endpoints that are continuous parameters, change from baseline at each on-treatment time point will be summarized with descriptive statistics. Inferential analyses may be performed. The distribution of responses to the ADCS-ADL-PI high-level function items will be summarized at each time point by treatment group.

Plots of mean (\pm SE) values and changes over time by treatment group will be provided for selected secondary efficacy endpoints. Change from the off-treatment baseline may also be summarized for each off-treatment time point and plotted.

For Global CDR ≥ 0.5 , the number and percentage of subjects meeting the criterion at any post-baseline on-treatment time point will be summarized. A similar summary based on off-treatment time points may also be provided. Descriptive statistics of the PACC change score may be summarized by treatment group for subjects who did and did not have the Global CDR ≥ 0.5 event at Month 12.

Association between the change from baseline in the CFI subject total score and the PACC change score, the CFI (actual) subject total score and the PACC change score, and the change from baseline in ADCS-ADL-PI subject total score and the PACC change score will be explored. Association between the functional measure and other cognitive measures will be similarly analyzed. Association between the total scores of subject-reported functional measures and the informant-reported functional measures will be explored as well.

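### SAP 5.1.2 fills a missing baseline PACC component with the Month 6 on-treatment value, which forces that component's Month 6 change to zero and puts a post-randomisation value into the baseline covariate

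*SAP*

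**What the plan says.** SAP 5.1.2 sets missing-data rules for the four scales that make up the PACC. For a scale missing at baseline but "observed at the next scheduled visit, the value at that visit will be used as the baseline value". The fill may reach back one visit at most.

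SAP 5.2.2 gives the schedule of these scales: during screening, "at the randomization visit, and every 6 months after randomization through Month 54". It defines each component as change from baseline divided by the baseline SD, and the PACC baseline score as the sum of the four standardised component baselines. It also sets a cap: "The PACC scores will be considered missing if more than 1 of its 4 components is imputed".

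SAP 5.2.3 lists the fixed terms of the MMRM, among them "education level, PACC baseline score, age at study entry, average hippocampal volume at baseline", and compares each dose with placebo at Months 6, 12 and 18. SAP 5.4.2 applies a similar model to each PACC component: "For each endpoint, baseline score in the model will be the baseline score for the given endpoint".

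Two other places affect how often the fill is used. SAP 2.4, Table 1, gives Baseline a window of Day -120 to Day 1, and where several visits fall in one window, "the visit closest to the target day will be used as the protocol visit for that visit window". Footnote i of the protocol's screening Time and Events Schedule says the PACC and other cognitive tests "must be performed once during the screening period but (1) prior to Step IV assessments, (2) no later than Day -20".

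**The concern.** A baseline should be measured before randomised treatment can affect it. The protocol places the baseline PACC on Day 1 before dosing. A Month 6 value has had about six months of assigned drug or placebo behind it, so using it as baseline removes whatever treatment did to that component in the period being compared. It also makes a model covariate depend on treatment.

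The cap in SAP 5.2.2 does not prevent this, because it admits a PACC score with one filled component. It is stated for PACC scores only. SAP 5.4.2 states no cap for the four component models, so a subject missing several Day 1 components could enter each of those models with a Month 6 change of zero.

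The PACC contrasts and the component models are among the between-group cognitive comparisons that the amended SAP still plans. A pre-dose screening value of each component is also scheduled for every subject.

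**Working it through.** **Which visit supplies the value.** The next visit of any kind after Day 1 is Week 2, but no PACC is given then. The rule can work only if it means the next visit at which that scale is scheduled. SAP 5.2.2 and Protocol 9.2.1 both make that Month 6.

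**One subject.** Let B be the true baseline of a component and X6, X12, X18 its later values. With B replaced by X6:

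- Month 6: (X6 - X6)/SD = 0, whatever the true change.
- Month 12: (X12 - X6)/SD, and Month 18: (X18 - X6)/SD. Both lose the first six months.
- The PACC baseline score contains X6/SD in place of B/SD.

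Illustration with assumed Month 6 changes of -0.25, -0.25, -0.25 and -0.50 SD: the true PACC change is -1.25. Filling one of the first three baselines gives -1.00. Filling the fourth gives -0.75.

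**Group difference, PACC.** The plan gives no figure for the share of subjects affected, so assume p = 1% to 10%, equal across arms (557 × 0.01 ≈ 6 and 557 × 0.10 ≈ 56 of the 557 randomised). Assume also that each component gains an effect d per six months, and let k = 1, 2, 3 for Months 6, 12, 18.

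- True difference: 4kd. Loss from filling one component in a share p: pd.
- Unadjusted shrinkage: pd/(4kd) = p/(4k).
- With the contaminated baseline as covariate: its between-arm shift is pd, and the within-arm slope of change on baseline is about -(1 - r), where r is the test-retest correlation. The adjusted difference is about 4kd - pd + (1 - r)pd = 4kd - rpd, so shrinkage is about rp/(4k).

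| | Month 6 | Month 12 | Month 18 |
|---|---|---|---|
| Unadjusted, p = 1% | 0.25% | 0.13% | 0.08% |
| Unadjusted, p = 10% | 2.5% | 1.25% | 0.83% |
| Adjusted, p = 10%, r = 0.6 (assumed) | 1.5% | 0.75% | 0.5% |
| Adjusted, p = 10%, r = 0.8 (assumed) | 2.0% | 1.0% | 0.67% |

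A simulation at Month 6 with p = 10% agrees: 2.5% unadjusted, and 1.5% (r = 0.6) and 2.1% (r = 0.8) adjusted.

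**Component models.** If a share q has that component filled, the unadjusted shrinkage is qd/(kd) = q/k. Spreading p = 10% evenly over four components gives q = 2.5%, hence 2.5%, 1.25% and 0.83%. An extreme q = 10% gives 10%, 5% and 3.3%.

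**Absolute scale.** As an assumption, scale the design difference of 0.49 at Month 54 (SAP 1.4) linearly to Month 6: 0.49 × 6/54 = 0.054. The largest PACC shrinkage, 2.5%, is then 0.054 × 0.025 ≈ 0.0014 units. With 557/3 ≈ 186 per arm and the SAP's SD of 2.44 (a Month 36 figure), the standard error of a difference is 2.44 × √(2/186) ≈ 0.25. The bias is about 0.5% of one standard error, or about 1% if the Month 6 SD is half as large.

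**Direction.** It is toward zero when component effects share a sign, but not always. With assumed effects of +0.1, -0.2, -0.2, -0.2 (sum -0.5) and only the first component filled, an affected subject's expected difference becomes -0.6.

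**The case against.** The strongest objection is that the rule may almost never be used. The screening PACC, done by Day -20, normally lies inside the Day -120 to 1 window. If that window works scale by scale, the screening value already serves when Day 1 is missing. This reading is likely: the CFI is assessed "5 to 10 days before randomization, then annually after randomization through Month 48", so choosing only the Day 1 visit would leave it without a baseline. But the selection rule in SAP 2.4 is worded by visit, and on that wording the Day 1 visit is chosen and the screening visit set aside. The SAP does not settle the matter. Either way the fill is not needed: it is redundant on the first reading and passes over a pre-dose value on the second.

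The objection on size also stands. No document supports p or q as high as 10%. The Day 1 PACC precedes randomisation, and SAP 5.4.1.4 prorates an MMSE with fewer than 10 missing items, so a wholly missing component should be uncommon. SAP 1.3 and 5.1.1 make all comparisons exploratory, with no formal testing. These points lower the priority of the change but do not make the rule correct.

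SAP 5.2.3 describes its model as based on observed data, which could be read as keeping filled values out. For the PACC this is hard to reconcile with the cap in 5.2.2, which has a purpose only if some imputed components enter. For the component models the question is open.

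The screening PACC is an imperfect baseline. It is a practice session, and Protocol 9.2.1 gives it a different Logical Memory paragraph. That is a real cost. Unlike a Month 6 value, though, it cannot carry a treatment effect.

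**Conclusion.** The concern holds. From the SAP's own definitions, every use of the backward fill sets a component's Month 6 change to zero, shortens its later changes by six months and makes the baseline covariate partly an on-treatment outcome. None of that depends on an assumption.

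The size does depend on assumptions, chiefly the unstated share affected, equal component effects and linear divergence. Within the range shown the bias is negligible beside the sampling error and would not change a conclusion. The reason to correct it is that the SAP states an invalid baseline definition that is easy to repair.

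**What to change.** In SAP 5.1.2, delete the backward fill. Add a sentence stating that the baseline of each PACC component is its last pre-dose value within the SAP 2.4 Baseline window: Day 1, or the screening value if Day 1 is missing. If no pre-dose value exists, that component's change and the PACC change are left missing. This also settles whether the window works scale by scale, and it covers the component models in SAP 5.4.2. Reporting the number of subjects per arm without a Day 1 value for a component would show how much this matters.

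The edit is one sentence removed and one added. A few PACC scores become missing at every visit, which discards that subject's three observed components. Where a screening value is used, the change includes a first-exposure practice effect and, for Logical Memory, a change of paragraph. Both are expected to be equal across arms, but they add noise. If the sponsor prefers not to use a practice session as baseline, deleting the fill alone removes the defect, with somewhat more missing data.
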